- Enrollment as AF or AT –for MARS-AF trial only.
- Pre-existing low voltage scar and extent of low-voltage scar after ablation procedure (divided in tertiles).

Primary Outcome. Hypothesis tests for the equality of two proportions (unpooled standard errors) will be employed for determining whether or not the VOM success rate is significantly greater than the success rate for PVAI. The test statistic is a z-score which is standard normal distributed and the relevant lookup critical values (percentage points) are listed in the interim analysis section for group sequential designs. From a post-hoc perspective, we may use the stratified Mantel-Haenszel odds ratio test of proportions if we learn that success rates track with a particular covariate, such as LA volume or AF duration, and the strata weights are not highly imbalanced.

Secondary Outcomes. The secondary outcomes are listed below along with their corresponding storage location (various tables or Excel .csv files on output after report generation). Model building strategies (MBS) will be employed using univariate and multivariable regression models for post-hoc analyses of secondary outcomes. During MBS, univariate predictors whose $p < 0.25$ will be selected as multiple variable model candidates. MBS regression methods may include linear, logistic, Poisson, and Cox proportional hazards (PH) along with regression diagnostics using the relevant goodness-of-fit criteria, residuals, variance inflation factors (VIF), ROC-AUC, and assumption-checking techniques (e.g. normally-distributed standardized residuals for linear regression). Regression diagnostics for linear regression will include estimation and filtering of overly influential records based on residuals, standardized residuals, deletion residuals, Cook's distance, leverage, DFFITS, DFBETAS, and VIFs. Regression diagnostics for logistic and Poisson regression will include filtering on Pearson, deviance, and leverage residuals and the Hosmer-Lemeshow test for logistic regression GOF. Cox PH regression diagnostics will include Schoenfeld and Nelson-Aelen residuals, and possible employment of stratified models when the PH assumption fails.

The table below lists the primary outcomes which are to be analyzed during each interim analysis, as well as the secondary outcomes which will be analyzed and reported prior to all DSMB review meetings.

Primary Endpoints	EDC Pages	Data Fields

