8. Incidence and mechanisms of atrial flutters.	
 12 lead ECG page AE page Evaluation for repeat procedure page 	
 Date of occurrence Type of flutter (typical vs atypical)
9. Cardiovascular hospitalizations and QOL.	
 Hospitalizations SAEs QOL 	
 Total # of CV related hospitalizations QOL score

Use of propensity scores in multivariate models. An ideal goal for observational etiological

studies is to allocate randomly subjects into different treatment groups in order to guarantee on average that there are no systematic differences in covariates between groups.¹²⁰ After randomization, there is nevertheless a possibility for observing large differences in confounders which may lead to bias in results. The propensity score provides a scalar summary of covariate information and is defined as the propensity (probability) that a subject's covariate profile represents subjects truly assigned to a given treatment group. Propensity scores based on significantly different confounder variables can be used to create a quasi-randomized experiment with adjustment to the treatment effect. We will assess the role of propensity scores in prediction models in order to reduce the effects of baseline factors that may be significantly different among subjects in different treatment groups. Firstly, we will identify baseline covariates which are significantly different across treatment groups (using t-tests with skew-zero transformed covariates or Mann-Whitney tests). Significant covariates will be incorporated into a logistic regression model ($y=0$ PVAI, 1-VOM-PV) to generate subject-specific logits, which are normally-distributed.^{121, 122} Treatment-subject-specific logits will then be used for matching subjects across the treatment groups in order to construct a sample of subjects with balanced covariates. We suspect that propensity matching will not be required to tackle the problem of extreme confounder differences, but will nevertheless evaluate the effect of propensity matching prior to logistic regression to determine treatment effect possibly adjusted for age.

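### Supportive propensity matching on baseline covariates that differ significantly between randomised arms should give way to one pre-specified adjusted model per trial; the primary test is not affected

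*Combined protocol and SAP*

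**What the plan says.** The primary analysis is in section 6.0, Statistical Analyses, Primary Outcome: "Hypothesis tests for the equality of two proportions (unpooled standard errors) will be employed". It is unadjusted. For covariates, the same paragraph offers only an optional step: "From a post-hoc perspective, we may use the stratified Mantel-Haenszel odds ratio test of proportions".

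The propensity paragraph comes later, after the table of secondary endpoints. It describes a sequence:

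1. "Firstly, we will identify baseline covariates which are significantly different across treatment groups", by t-test or Mann-Whitney test.
2. The significant covariates enter a logistic model for treatment arm.
3. The resulting logits "will then be used for matching subjects across the treatment groups in order to construct a sample of subjects with balanced covariates".

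On whether this will be used, the authors first state that they do not expect to need it: "We suspect that propensity matching will not be required to tackle the problem of extreme confounder differences". They then commit to looking at it all the same, with the stated intention to "evaluate the effect of propensity matching prior to logistic regression to determine treatment effect possibly adjusted for age".

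The paragraph gives no significance level, list of candidate covariates, matching ratio, caliper, replacement rule or handling of unmatched patients. No covariate-adjusted treatment effect is pre-specified anywhere else. The plan does name age, gender, baseline AF duration and baseline LA volume as example predictors in its imputation model (section 6.0, Missing data), and section 5.1 stratifies the MARS randomisation by flutter versus AF recurrence.

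**The concern.** Matching on a propensity score is a remedy for confounding in observational data. Here the arms are randomised, so a significant baseline difference between them is a chance finding, and its p-value says nothing about whether the covariate affects outcome. A weakly prognostic covariate that happens to reach significance would drive the matching. A strongly prognostic one that falls just short would be ignored.

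Three consequences follow. The adjusted estimate depends on which covariates cross a threshold in the observed data. With no significant covariate there is no score and the procedure has no defined output. And matching can discard randomised patients, at a cost in precision. What is at stake is the quality of the supporting evidence: this is the plan's only stated route to an adjusted effect when the arms look unbalanced.

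**Working it through.** **Inputs.** VENUS: 180 VOM-PV and 156 PVAI, success rates 0.56 and 0.38, three looks with boundaries 3.953, 2.543 and 2.011 (section 6.0 B, Tables 5 and 6). MARS: 37 and 32 (synopsis), or 33 and 33 (section 6.0 C, Table 9), success rates 0.76 and 0.42.

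**The plan's own figure.** Simulating the three-look unpooled z-test (400,000 runs) gives power 0.910 against the stated 0.909. The closed form at the final boundary agrees: 0.18/0.0537 − 2.011 = 1.34, power 0.91. Nothing in the propensity paragraph enters this calculation.

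**Chance significance.** Assume a 0.05 threshold and k independent covariates under sound randomisation. The chance that at least one is significant is 1 − 0.95^k:

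- k = 4: 1 − 0.8145 = 19%
- k = 10: 1 − 0.5987 = 40%

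In the remaining 81% or 60% of trials there is nothing to match on.

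**Patients lost in VENUS, assuming 1:1 matching without replacement.** At most 156 pairs can be formed, so at least 180 − 156 = 24 patients are dropped: 24/336 = 7.1% of the trial, 24/180 = 13% of the VOM-PV arm.

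**Nominal standard error of the difference.** SE = √(0.56×0.44/n₁ + 0.38×0.62/n₂) = √(0.2464/n₁ + 0.2356/n₂).

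| Sample | Dropped | SE | Change |
|---|---|---|---|
| 180 / 156 | 0 | 0.0537 | – |
| 156 pairs | 24 (7.1%) | 0.0556 | +3.6% |
| 140 pairs | 56 (16.7%) | 0.0587 | +9.4% |

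The 156-pair row is the best case for 1:1 matching. The 140-pair row comes from the simulation below, with an assumed caliper.

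**Simulation.** There were 3,000 trials per scenario at the VENUS sizes. The following are assumptions, because the plan states none of them: 8 independent normal covariates of which 3 may be prognostic, selection by t-test at p<0.05, and greedy 1:1 matching with a caliper of 0.2 SD of the logit. The comparator was a logistic model pre-specified on the 3 potentially prognostic covariates and standardised to a risk difference. The matched effect was taken as the plain difference in proportions, without a logistic regression after matching. About a third of trials had a significant covariate, and in those about 140 pairs remained. SD of the estimated risk difference in those trials:

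| Prognostic strength (log OR per SD, each of 3) | Unadjusted, all patients | Pre-specified adjustment | Matched |
|---|---|---|---|
| 0 | 0.052 | 0.052 | 0.058 |
| 0.4 | 0.054 | 0.050 | 0.056 |
| 0.7 | 0.056 | 0.048 | 0.056 |

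**How large a model MARS can carry.** Expected failures at 37/32: 37×0.24 + 32×0.58 = 8.9 + 18.6 ≈ 27. At 33/33: 7.9 + 19.1 ≈ 27. Arm plus five covariates would have 27/6, about 4.6 failures per coefficient. Arm plus the AF/flutter stratum has 27/2, about 14.

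**The case against.** The strongest reply is that this is an exploratory paragraph about an analysis the authors expect not to need, and that no primary result depends on it. That stands. Four stronger readings are tempting, and the documents do not support them.

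- *The trial loses power, or the matched result could displace the primary one.* A z-test on 156 or 140 VENUS pairs would have power of about 89% or 85% at the final boundary, but no such test is planned. The primary test is fixed, and nothing lets a matched estimate replace it.
- *Matching will certainly be carried out.* The plan commits to evaluating it, but without a significant covariate there is no score, so in effect it is conditional.
- *At least 24 patients must be lost.* This follows only for 1:1 matching without replacement. Full or variable-ratio matching could keep everyone. The stated aim of constructing a sample reads more naturally as a subset, but the plan does not settle it.
- *Matching always costs precision.* Against the unadjusted full-sample estimate it does not: with strongly prognostic covariates the two were about equal (0.056 and 0.056). The deficit was consistent only against pre-specified adjustment.

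It is also fair to say that imbalance need not be pure chance among analysed patients, because section 6.0 A excludes those who cannot be classified. That is a reason to deal with missing outcomes directly. Baseline significance tests do not address it.

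**Conclusion.** The point holds as a cheap improvement to a supportive analysis. Choosing covariates by significance tests between randomised arms is the wrong criterion. The procedure is undefined when nothing is significant, and its remaining settings are unstated. The primary z-test and its 91% power are not in question.

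The size is modest and rests on assumptions. With 1:1 matching without replacement, the nominal SE in VENUS rises by at least 3.6%, and by about 9% with the assumed caliper. Under the simulated covariates, matching was less precise than pre-specified adjustment in every scenario (SD 0.056–0.058 against 0.048–0.052). The 19% and 40% chance-significance figures assume a 0.05 threshold and independent covariates. Correlated covariates or another threshold would change them.

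**What to change.** Delete the baseline significance tests and the matching from section 6.0. Keep the unadjusted z-test as primary.

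Pre-specify one supportive logistic model per trial, fitted to all classifiable randomised patients by randomised arm, and report the standardised risk difference with its confidence interval:

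- **VENUS:** arm plus age, sex, AF duration and LA volume. The plan names these four only as an imputation example, so adopting them for adjustment is a judgement for the trial team to confirm before unblinding.
- **MARS:** arm plus the AF/flutter randomisation stratum only. About 27 expected failures are too few for more.

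Repeat each model with the multiple imputation already planned under Missing data. The imputation model should contain every term of the analysis model, including arm, which the plan's example list does not mention.

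The cost is SAP wording and a little more analysis work. The VENUS covariates and the MARS stratum are already named in the plan, so no new data are needed. The one constraint is that the covariates must be fixed in advance, so the team gives up the freedom to respond to an imbalance seen later.

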6.0 STATISTICAL CONSIDERATIONS

A) Assumptions.

Single-procedure versus multiple-procedure success. Our initial preliminary data suggested an overall procedure success of 45% in patients undergoing PVAI and 61% for those undergoing VOM-PV (difference of 16%). This included patients with repeat procedures performed in some, but not all of the failed procedures (45% all patients in the PVAI group and 30% in the VOM-PV group). **The single-procedure success was 38% in patients undergoing PVAI and 56% in patients undergoing VOM-PV** (difference of 18%). Thus, the endpoint of single-procedure success is likely to show greater differences amongst groups.

Mortality. The expected mortality is low in this study as it has been in AF ablation trials.

Mortality will be recorded as a safety endpoint.

One-year follow-up time. In previous versions of the protocol, additional follow-up time (up to 15 months) was included in the VENUS trial, in order to accommodate for appropriate follow-up of patients undergoing repeat procedures. Therefore, a trial duration of 12 months is sufficient if just single-procedure success is the primary efficacy endpoint. Procedural failures (events counted as the primary efficacy endpoint) occur mostly during the first year. Additionally, 12-month follow-up is consistent with the recommendations for clinical trials in AF by the HRS/EHRA/ECAS Catheter and Surgical Ablation consensus document.²

Unknown classification as success or failure. Patients who cannot be classified as successes or failures on the primary efficacy endpoint will be excluded from the primary analysis.

B) VENUS Group Sequential Clinical Trial Design

Power and sample size determination. Group sequential two proportions power analysis using simulation was performed using PASS V12 (Kaysville, UT). The following assumptions were made:

- Response rate in PV-VOM: $p_1=0.56$
- Response rate in PVAI: $p_2= 0.38$
- Hypotheses: $H_0: p_1= p_2$; $H_1: p_1 \neq p_2$
- Test Statistic: Z-Test (Unpooled)
- Zero Adjustment Method: None
- Alpha-Spending Function: O'Brien-Fleming Analog
- Beta-Spending Function: None
- Futility Boundary Type: None
- Number of Looks: 3
- Simulations: 100000

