Missing data. The critical piece of data required for endpoint analysis is the electrocardiographic event monitor. Failure to comply with wearing the monitor will lead to missing data. We request patients to wear monitors for 1–month. However, only a minimum of 1-week of monitored time is required for Endpoint assessment. Patients with less than 1 –week of monitoring will be considered as missing data. Patients who die before then study end will be considered not to have a response to treatment. For patients with missing primary outcomes, we will perform multiple imputation (MI) based on Monte Carlo Markov chain (MCMC) methods (Refs 1-3). MI will only be used for dealing with missing data as a secondary analysis tool of the primary endpoint. In Stata, MI is available for many procedures, especially the regression modules (linear, logistic, Poisson, Cox PH). MI can be performed to iteratively impute central estimates of missing outcome measures based on subjects' covariate patterns. The most straightforward example can be envisioned in this study, where logistic regression with MI is employed to train a model based on primary outcome (0-failure,1-success) as the dependent variable and age, gender, baseline AF duration, and baseline LA volume as independent predictors to impute $P(y=1|x)$ for subjects with missing primary outcome.

Sensitivity analysis. Following methods introduced in Proschan et al. (Ref 4), we simulated success rates for patients with missing 12-month outcomes in VOM and PVAI arms for VENUS and MARS at 33%, 66%, and 100% information time (looks 1-3). $B=100,000$ iterations were used with proportions of $P_m=0, 0.05, 0.10, 0.15$, and 0.2 representing the amount of missing data in both VOM and PVAI arms. At look k , let the success rate in the VOM arm be p_{1k} and the success rate in the PVAI arm be p_{2k} , n_{1k} and n_{2k} the number of patients accrued in the VOM and PVAI arms, $n_{1k}^m = n_{1k}P_m$ and $n_{2k}^m = n_{2k}P_m$ the number of patients in VOM and PVAI arms with missing outcome data, and $n_{1k}^0 = n_{1k} - n_{1k}^m$ and $n_{2k}^0 = n_{2k} - n_{2k}^m$ the number of patients in VOM and PVAI arms without missing outcomes. Next, for VOM patients with missing

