	0.15	1.000	1.000	0.977	0.903	0.619
	0.2	0.984	0.939	0.734	0.516	0.369
0.86	0	1.000	1.000	1.000	1.000	1.000
	0.05	1.000	1.000	1.000	1.000	1.000
	0.1	1.000	1.000	1.000	1.000	1.000
	0.15	1.000	1.000	1.000	0.981	0.913
	0.2	1.000	0.986	0.944	0.852	0.619

D) Stopping rules. The trials will be stopped if one of the following occurs:

- Futility/efficacy boundaries reached. As illustrated in Figures S1 and S2, if the upper or lower boundary is reached at the 1/3 or 2/3 data assessment for beneficial efficacy or futility respectively, the trial will be evaluated for early termination.
- Safety. Events will be reported to FDA, NHLBI, and DSMB according to FDA/OHRP requirements and NHLBI adverse event and unanticipated problem reporting policy. Expedited reporting will occur within 7 days of initial receipt of information for fatal or life-threatening unexpected serious reactions and within 15 calendar days for non-fatal, non-life threatening unexpected events. The DSMB will otherwise evaluate overall safety events on a bi-annual basis. An excess of **procedural** adverse events attributable to study procedure will be evaluated for early termination. Procedural adverse events include those that occur within 24 hours of the procedure or those that may be delayed but procedure-related (atrio-esophageal fistula or delayed pericardial effusion). The following are expected to be rare. One event may occur by chance in either treatment groups. Two of the same events in either arm will trigger consideration for study termination after detailed case review:
 - Mortality.
 - Stroke-Transient ischemic attack or systemic embolus.
 - Pericardial effusion requiring drainage

- Raghunathan, T. E., J. M. Lepkowski, J. Van Hoewyk, and P. Solenberger. 2001. A multivariate technique for multiply imputing missing values using a sequence of regression models. *Survey Methodology* 27: 85–95.
- Rubin, D. B. 1987. *Multiple Imputation for Nonresponse in Surveys*. New York: Wiley.
- van Buuren, S. 2007. Multiple imputation of discrete and continuous data by fully conditional specification. *Statistical Methods in Medical Research* 16: 219–242.

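### The multiple-imputation text for missing primary outcomes describes filling in a fitted probability from a model without treatment arm; both need correcting together, in a secondary analysis only

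*Combined protocol and SAP*

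**What the plan says.** Section 6.0, paragraph on unknown classification, sets the primary analysis: "Patients who cannot be classified as successes or failures on the primary efficacy endpoint will be excluded from the primary analysis". The Missing data paragraph of the same section then adds, for patients with a missing primary outcome, that "we will perform multiple imputation (MI) based on Monte Carlo Markov chain (MCMC) methods (Refs 1-3"). The cited sources include "Multiple Imputation for Nonresponse in Surveys". The role is limited: "MI will only be used for dealing with missing data as a secondary analysis tool of the primary endpoint".

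Two sentences describe what is imputed. The first says that the method can "iteratively impute central estimates of missing outcome measures" from each patient's covariates. The second is a worked example: a logistic model for success or failure, with "age, gender, baseline AF duration, and baseline LA volume as independent predictors", is used to impute P(y=1|x) "for subjects with missing primary outcome". Treatment arm is not among the predictors. The paragraph does not mention 0/1 draws, the number of imputations or a rule for combining them.

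**The concern.** A fitted probability is a conditional mean, not a possible outcome. Filling it in leaves out the 0/1 variation of the missing outcome. Even if the coefficients are redrawn for each data set, little between-imputation variance is added. The analysis then behaves as if every randomised patient had been observed, which is not what the cited multiple-imputation method does. An analyst who follows the example and one who follows the references would report different intervals.

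This is the planned secondary analysis for patients whom the primary analysis drops. It is meant to show what the missing outcomes do to the result. As described, it reports a nominal standard error smaller than that of the complete cases without any added information, and the omitted arm pulls the estimated effect towards zero.

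**Working it through.** **Inputs from Section 6.0.** VENUS 180 + 156; success 0.56 against 0.38; unpooled Z, two-sided 0.05; boundaries 3.953, 2.543 and 2.011; missing share f from 0 to 20% per arm in the sensitivity grid (no expected rate is given).

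**Assumptions.** Missing completely at random, same f in both arms; four covariates with log-odds 0.3 each; equal true rates of 0.46 for the null case.

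**Step 1, the plan's own figure.** One million simulated trials give cumulative power 0.036, 0.578 and 0.910 at the three looks. Table 6 gives 0.033, 0.033 + 0.547 = 0.580, and 0.909. The design reproduces. The plan states no standard error or power for the imputation analysis.

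**Step 2, nominal standard error.** With fill-ins counted as observed, SE = √(0.56×0.44/180 + 0.38×0.62/156) = √(0.001369 + 0.001510) = 0.0537. For complete cases at f = 0.20 it is 0.0537/√0.80 = 0.0600.

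**Step 3, predictors as listed (no arm).** Fill-ins have about the same mean in both arms and cancel, so the difference is about (1−f) times the complete-case difference: 0.80 × 0.18 = 0.144. Under equal rates the full-size SE is √(0.46×0.54×(1/180 + 1/156)) = 0.0545. The estimator's own SD is about √0.80 × 0.0545 = 0.0488. The reported SE exceeds it, the effective critical value is 1.96/0.894 = 2.19, and type I error is about 2.8%.

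**Step 4, arm added, probabilities still filled in.** The difference is about the complete-case one, with SD 0.0545/√0.80 = 0.0610. The SE ratio is √(1−f) = 0.894, the effective critical value is 1.96 × 0.894 = 1.75, and type I error is 8.0%. At 5, 10 and 15% missing it is 5.6, 6.3 and 7.1%.

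**Step 5, simulation at 20% missing** (6,000 trials per setting; 20 imputations where multiple). Type I error and SE/SD are under equal rates; the last three columns are at 0.56 against 0.38. Tests use 1.96.

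| Method | Type I error | Reported SE / true SD | Estimate | Coverage of true difference | Power |
|---|---|---|---|---|---|
| Complete case | 5.2% | 0.0607 / 0.0609 | 0.180 | 94.7% | 84.2% |
| Fitted probability, no arm | 3.1% | 0.0543 / 0.0493 | 0.144 | 92.0% | 77.5% |
| Fitted probability, arm | 8.1% | 0.0543 / 0.0605 | 0.180 | 92.0% | 88.5% |
| Fitted probability, coefficients drawn, Rubin's rules, arm | 7.3% | 0.0556 / 0.0603 | 0.179 | 92.7% | 87.6% |
| 0/1 draws, Rubin's rules, no arm | 1.9% | 0.0592 / 0.0495 | 0.144 | 94.6% | 71.9% |
| 0/1 draws, Rubin's rules, arm | 5.3% | 0.0603 / 0.0605 | 0.179 | 94.6% | 84.3% |

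At 10% missing, the fitted probability gives 6.3% type I error with arm. Without arm it gives 4.0%, an estimate of 0.161 and coverage of about 94.5%. Repeat simulations at 20% missing gave 6.9% and 8.3% type I error with arm, and 92.1% and 92.4% coverage without arm.

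**The case against.** The best reply is that the binding sentence promises MCMC multiple imputation with standard references, while the sentences on fitted probabilities are worded as what can be done and as an example. A competent programmer may well make proper draws. The sensitivity simulation later in the section does use binomial draws for missing outcomes, so the idea was familiar. This stands in part: the text contradicts itself and does not establish that no draws will be made. But the only description of the imputed value, and the only model given, point the wrong way.

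A reader might infer more than the documents support:

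- **That the plan as written understates the standard error and inflates type I error.** It does not. With the four listed predictors, the reported SE is below the complete-case SE but above the estimator's own SD, and the test is conservative. Inflation appears only once arm is in the model.
- **That this analysis would look more convincing than the primary one.** With the listed predictors it looks weaker at the design effect: Z is about 0.144/0.0538 = 2.7, against 0.180/0.0597 = 3.0 for complete cases (20% missing).
- **That error rates above 10% are in play.** Those need the sample variance of the fractional fill-ins (11.4% in the simulation, with arm, at 20% missing). The plan's unpooled Z uses p(1−p)/n.
- **That the primary result is at risk.** Imputation is expressly secondary, so the primary test, its boundaries and the sample size are untouched.

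**Conclusion.** The point holds as a contradiction between the named method and the described one, together with an imputation model that omits arm. Which harm appears depends on the model used. As listed, it is shrinkage of the effect and about 92% coverage at 20% missing, with little loss of coverage at 10%. With arm added and nothing else changed, it is a standard error about 10% too small and type I error of about 6% at 10% missing and 7-8% at 20%. Neither repair works alone: draws without arm leave the estimate at 0.144 and cut power to 72%, while arm without draws makes a conservative test anti-conservative.

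The sizes rest on data missing completely at random, equal missingness in both arms and modest covariate effects. The 20% figure is the top of the plan's grid, not a forecast. Only VENUS was computed, although the paragraph is not limited to it. The text should be corrected before the analysis is run.

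**What to change.** Replace the two descriptive sentences with a specification such as this: each missing primary outcome is drawn as 0 or 1 from the posterior predictive distribution of a logistic model, with the coefficients also drawn; the model contains treatment arm alongside age, gender, AF duration and LA volume (or imputation is done separately by arm); a fixed number of imputations, for example 50, is used; the difference in proportions and its variance are combined by Rubin's rules.

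The cost is a change of wording; standard software does this already. The secondary interval becomes slightly wider than under fill-in. At 20% missing and the design effect, the half-width is about 1.96 × 0.0594 = 0.116, against 1.96 × 0.0538 = 0.105, and close to the complete-case 1.96 × 0.0597 = 0.117.
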